STU#: 00212165

PROTOCOL TITLE: Targeted Melanoma Detection with Skin Self-Examination During COVID-19 Restricted Physician Access

PRINCIPAL INVESTIGATOR:

[name]
Northwestern University Feinberg School of Medicine
Department of Dermatology
[name]
[name]
[contact]
[contact]

RESEARCH PERSONNEL:

[name], MS
[name], BS

STATISTICIAN:

[name]
Professor of Preventive Medicine
Northwestern University Feinberg School of Medicine

VERSION DATE:

April 2, 2020

NCT04420273

STUDY SUMMARY:

The purpose and overarching aim of this study is to reduce melanoma mortality by improving early detection of melanoma with skin self-examination among people who self-identify as being at risk. Self-management of melanoma detection with skin self-examination (SSE) depends on ready access to dermatologists when a concerning mole is detected. In March 2020, the Illinois stay at home order (COVID-19) removed ready physician access and prohibited non-essential health care. Additionally, there was uncertainty about when regularly scheduled health care would resume. This submission seeks to explore the feasibility of at-home non-invasive mole self-sampling for those with a concerning mole with the intention of providing recommendations about the need for the mole to be biopsied.

OBJECTIVES:

Aim 1: To assess the effectiveness of targeted melanoma detection (TMD) with SSE education delivered remotely to women who had a screening mammogram.

The effect of TMD with SSE education on a) SSE performance, b) identification of concerning moles, c) time between noticing a concerning mole, requesting a mole self-sampling kit and receiving health care, and d) SSE sustainability in comparison with controls will be assessed among women served by Northwestern Medicine in one rural community and one metropolitan community. Health care providers' (HCPs) clinical/pathologic assessment of concerning moles will be identified in the Northwestern Medicine electronic health record (EHR) system.

Exploratory Aim: To assess the feasibility of self-sampling concerning moles for gene assay.

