Self-sampling kits will be sent to women who identify concerning moles and chose to perform self-sampling rather than watch the mole for change in a month. The blinded samples will be sent to DermTech, Inc., a CLIA laboratory, for analysis and the results reported directly to the PI. The PI will give the results to the participant, make a recommendation about the need to obtain a biopsy of the mole, offer to provide a referral to local HCPs, and send the laboratory results to the HCP selected by the participant. Anxiety/cancer worry will be assessed monthly to compare a) baseline measures, b) initial SSE and c) monitoring concerning moles for change.

Knowledge gained from this study may be helpful to other health care systems serving at-risk women and their families in locations with limited access to physicians, especially dermatologists.

BACKGROUND:

Early detection of melanoma remains a crucial component of effective treatment to reduce the mortality and morbidity of melanoma and the costs of melanoma care. In the United States (US), melanoma incidence has increased by 270% between 1973 and 2002 and is projected to continue rising in the US with doubling of newly diagnosed cases by 2030.^{1,2} Melanoma is the sixth most common cause of cancer in women in the US (fifth in men). There will be an estimated 100,350 new cases and 6,850 deaths in 2020.¹¹ Melanoma predominantly occurs in non-Hispanic Whites with a history of unprotected occupational or recreational sun exposure; however, indoor tanning by

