make 80% of all health care decisions for the family, shared the SSE brochure with relatives.^{4,6,29,30}

The *long-term goal* of this research is to reduce melanoma mortality by improving self-management of early detection of melanoma. Reduced mortality cannot be proven without effective structured melanoma SSE with partner assistance. One way to achieve partner-assisted SSE is to deliver a uniform self-management program to women who self-identify as at-risk, perform SSE and seek appointments with HCPs for concerning moles. In the absence of ready physician access due to COVID-19, we will test the feasibility of at-home mole self-sampling with a non-invasive adhesive patch used to acquire surface cells of the mole. Our *primary objective*, assessing effectiveness of a SSE education with partner assistance among at-risk women, extends the evidence-based SSE intervention developed among melanoma survivors and their skin check partners (R01CA154908)⁶ and delivers the program to women who had a screening mammogram, which demonstrated the individuals' commitment to health promotion and cancer screening.

STUDY ENDPOINTS:

Aim 1

Primary outcome:

Effectiveness of TMD with SSE will be defined as SSE performance. Further measures of fidelity will be assessed by:

- a) extent of body checked,
- b) recruitment of a skin check partner,
- c) time between noticing a concerning mole, requesting a mole self-sampling kit, and seeking HCP care for a concerning mole, and
- d) SSE sustained by monthly performance over 4 months.

Secondary Outcome:

The effect of TMD with SSE on seeking health care comparing intervention vs control groups for:

- a) inappropriate HCP appointments and skin biopsies for benign conditions, and
- b) appropriate HCP appointments for the clinical diagnosis of atypical (dysplastic nevus) or rule out melanoma and biopsy performed.

Exploratory Aim

Proof-of-concept Outcome:

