Research participants will self-sample concerning moles using a kit currently used in physician offices to obtain a sample (DermTech, Inc). DermTech, Inc. will perform analysis on up to 100 specimens and send the report to the PI. This report will include gene assay results or indicate if there are too few cells for analysis, which may reflect lack of self-sampling competency. If the initial sample has too few cells for analysis, then the instructions will be reviewed by telephone with the participant and an additional sample will be obtained. Time to initiation of mole self-sampling after identifying a concerning mole, number of kits returned for analysis, and adequate number of cells acquired will be assessed. Correlation with monthly SSE anxiety will be done.

STUDY INTERVENTIONS:

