If the option to see the HCP is selected, the research team will assist with locating one and will remind the subject that the HCP may not be available for some time. The study team will not cover the cost of seeing the HCP or cost of treatment recommended by the HCP. The non-payments details are explicitly stated in the consent document.

If the mole(s) requires a biopsy and/or treatment, the EHR will be reviewed to identify diagnosis codes of the mole and review HCP notes.

If throughout the 4 months of active engagement in skin self-examinations, a participant in the intervention arm indicates that they found a concerning mole on their skin check partner while performing a partner skin exam, an opportunity for the concerning mole of the partner to be self-sampled will be offered. For the self-sampling to occur, the subject (the skin check partner) would first be asked eligibility questions to ensure they are over the age of 18 and meet basic eligibility criteria. Once eligibility is established, the partner will be sent an electronic consent form, via REDCap, and complete and sign the form,

indicating they understand what is expected of them as a research participant and the information that was presented to them in the consent document. The same process will be followed for the skin check partner as is in place for the research subject.

Controls (Group 1) will receive a healthy lifestyle brochure and a healthy lifestyle postcard after consenting online and completing baseline assessments. After enrolling in the study, a baseline survey will populate in REDCap, and the subject will be able to download a healthy lifestyle brochure and the postcard reminder. Upon request, the brochure will be mailed. Each month, the subject will receive an email to complete the monthly survey and will receive healthy lifestyle text messages to their mobile phone. The survey they receive will mirror the survey of the SSE intervention arm; therefore, awareness of SSE will be expected to increase, and SSE may be initiated among controls. If a subject indicates that they have found a concerning mole on their monthly survey, the subject will be advised to reach out to their health care provider for further assessment. After completing the final monthly survey, controls will be offered the SSE brochure.

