Intervention participants who have selected the mole self-sampling kit will be invited to participate in a structured telephone exit interview. The exit interview will seek to obtain feedback from the participant on the process of mole self-sampling and gain feedback on study materials. Subjects will be asked, at time of consent, if the study team has permission to audio record the exit interview for purposes of data analysis. Subjects may opt out of the audio-recording portion of the study. The researcher will not share these recordings with anyone outside of the immediate study team. The recordings will remain in locked file cabinets and on computers with restricted and password protected access.

Anxiety will be assessed on monthly surveys. If enhanced anxiety regarding a concerning mole is indicated, a referral for psychological support will be made by PI, [name].

Out of the 500 women enrolled at each location, it is expected that 140 of the 1000 (14%) enrolled will identify a concerning mole.⁴

DATA AND SPECIMEN BANKING:

See Data Management. Specimens will not be banked.

SHARING RESULTS WITH PARTICIPANTS:

Results of the gene analysis from the cells captured by the adhesive patches will be provided to the PI, [name]. [name] will then inform the participant, in the form of a written report, if the mole is benign and nothing further needs to be done or if the mole needs to be biopsied. If requested, [name] will discuss the report with participants. Participants requiring a skin biopsy will be referred to a local HCP, who will receive the genetic analysis of the mole via fax from [name]. At the conclusion of the study, all participants will receive an email summary of the results.

The same process of sharing results applies to participants and their skin check partners who have a concerning mole to self-sample.

STUDY TIMELINES:

Subjects, both intervention and controls will be engaged with the research for 4 months. After 4 months of active engagement, follow-up communication will only occur via telephone or email to answer any incomplete questions on surveys or any questions that arise from evaluating the EHR of HCP visits regarding the concerning mole(s). All communication will be documented in the subject's file as a progress note.

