Subjects will be participating in an intervention that may enhance their awareness of their risk of developing skin cancer. All study participants will be provided with an email address and phone number to contact study staff in the event they have concerns. If a subject indicates they have a concerning mole, they will be provided with three options on how to address the mole. The research team will be in communication with the subject to ensure there are no questions or concerns regarding next steps. Because of the potential for the intervention to help the subject identify melanoma at a stage of development with the best prognosis, we feel that the potential benefits, in reduced morbidity and mortality, to the subject outweigh the risk of potential enhanced anxiety in discovering a suspicious mole. If subjects report high levels of anxiety, then a referral for psychological support would be made. We do not believe that subjects in this study will be exposed to any risk of physical or psychological harm as a result of either the intervention or research processes. Our measures do not assess individuals at risk of immediately harming themselves (e.g. suicide); therefore, we will not have to screen the data to potentially intervene with individuals who may be a risk to themselves.

POTENTIAL BENEFITS TO PARTICIPANTS:

Because of the potential for the intervention to help the subject improve their ability to detect melanomas in the early and potentially curable phase, they will reduce their risk of death from melanoma. We feel that the potential benefits in reduced morbidity and mortality to the subject outweigh the risk of potential enhanced anxiety in discovering that they are at risk to develop another melanoma. If subjects report high levels of anxiety, then a referral for psychological support would be made.

DATA MANAGEMENT AND CONFIDENTIALITY:

Data Management and Quality Control

Data will be collected via REDCap and by EHR data abstraction to populate the database. The subject number identifies the specimen on the case report form for gene sampling of moles. All databases are encrypted and stored on study specific servers at Northwestern University. Forms and database architecture will be set up during study preparation and launch. Only authorized study personnel can access these servers. Our data manager maintains data integrity and does fidelity checks and performs regular data checking for accuracy and completeness in coordination with the PI.

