Design, Analysis, and Power Calculation with Target Enrollment Justification

For the RCT, participants will be randomly assigned to receive the SSE intervention or control (healthy lifestyle) in a 1:1 ratio. This will result in approximately 500 participants in each group. The primary analysis will be intent to treat, with data imputed one of two ways. First, we will run a “worse-case scenario” where all drop-outs will be assumed to not be performing SSE. Second, we will create 5 imputed data sets for missing data based on all available data and analyze with PROC MIANALYZE to obtain valid statistical inferences. From previous work, we expect at least 60% retention at 4 months.

We will use GLMM with a logit link to test if the intervention affects the rate of SSE, while adjusting for the repeated measures within individuals over the first 4 months. Using these repeated measures, and assuming an autocorrelation of 0.9, a total sample of 1000 would enable us to detect an increase from 80% of SSE in the control group to 86.3% in the intervention group. Assuming only 10% discordance, a sample of 500 control women provides 80% power to detect an increase of 7%, while the remaining 3% cease SSE. Additional fidelity measures in Aim 2 will be combined to score an overall standardized fidelity score at each time. If the mean fidelity score is 80%, a sample of 500 women provide enough information to produce a 95% Confidence interval with a width of 0.09. The sample for 500 intervention women provides 80% power to detect declining fidelity or sustainability of monthly SSEs as a standardized slope of 0.13. The secondary outcome of seeking HCP appointments for a necessary mole will be analyzed with generalized linear models, as described above, but considering the outcome as “any HCP appointment” during the study time frame. Previous data suggests that approximately 14% of women should contact HCP for an appointment, and our sample of 1000 women provides 80% power to detect a baseline rate in the control group as small as 21%.

Plans for securing the data is in the “provisions to protect the privacy interests of participants” section of the protocol.

PROVISIONS TO MONITOR THE DATA TO ENSURE THE SAFETY OF PARTICIPANTS:

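### Anxiety and cancer worry are compared only across successive study stages; no intervention-versus-control comparison is specified, so a stage difference could reflect time or selection

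*Combined protocol and SAP*

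**What the plan says.** The group-level plans for anxiety are two sentences.

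- OBJECTIVES, Exploratory Aim: "Anxiety/cancer worry will be assessed monthly to compare a) baseline measures, b) initial SSE and c) monitoring concerning moles for change".
- STUDY ENDPOINTS, Exploratory Aim, after the self-sampling measures: "Correlation with monthly SSE anxiety will be done".

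On data collection, PROCEDURES INVOLVED says "Anxiety will be assessed on monthly surveys" without naming an arm. Of the controls it says "The survey they receive will mirror the survey of the SSE intervention arm". STUDY INTERVENTIONS describes the intervention-arm monthly item as one about anxiety linked to moles that are changing.

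Where a control comparison is intended, the protocol says so. Aim 1 lists SSE performance, identification of moles, time to care and, last, "d) SSE sustainability in comparison with controls will be assessed". The secondary outcome is introduced with "The effect of TMD with SSE on seeking health care comparing intervention vs control groups for" and covers appointments and biopsies. Anxiety is in neither list. The section on design, analysis and power specifies a model for SSE ("We will use GLMM with a logit link to test if the intervention affects the rate of SSE") and does not mention anxiety.

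RISKS TO PARTICIPANTS argues that the potential benefits "outweigh the risk of potential enhanced anxiety in discovering a suspicious mole". The same section says that no psychological harm is expected.

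**The concern.** Baseline, first SSE and monitoring of a mole follow one another in time. A difference between them is a before-after difference, and four things besides the intervention can produce one:

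- **Calendar time.** Enrolment is planned for June to August 2020 and surveys run to December 2020, in a trial built around restricted access to physicians.
- **Regression to the mean.** Women enter because they see themselves as possibly at risk, and some may enrol when their worry is above its usual level.
- **Repeated questioning.** The same topic is raised every month.
- **Selection.** Only women with a concerning mole, about 14% by the protocol's expectation, can reach the monitoring stage.

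A rising background trend could look like harm from SSE, and a falling one could hide harm. At stake is the empirical support for the protocol's own risk-benefit statement. About 1000 women are randomised 1:1, which would allow a test of whether SSE education changes anxiety, but the plan does not name that test.

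**Working it through.** **No planned figure to reproduce.** The protocol gives no anxiety scale, SD, effect size, alpha or power. The check has two parts: reading the text, and an illustration on assumed values.

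**Part 1: the text.** Every place that mentions anxiety or a control comparison falls into one of these groups:

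- anxiety across stages (OBJECTIVES);
- anxiety correlated with self-sampling (STUDY ENDPOINTS);
- individual handling of raised anxiety by referral or contact with the investigator (PROCEDURES INVOLVED, RISKS TO PARTICIPANTS, the safety-monitoring section);
- control comparisons of other outcomes (Aim 1, secondary outcome, analysis section).

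None combines anxiety with a comparison between arms.

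**Part 2: illustration.**

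Inputs from the protocol:
- about 500 women per arm;
- at least 60% retention at 4 months, so 0.60 × 500 = 300;
- 14% expected to identify a concerning mole, so 0.14 × 500 = 70 in the intervention arm, or 0.60 × 70 = 42 after the same retention.

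Assumptions:
- moles are found equally often in both arms (doubtful, since mole identification is an outcome that the intervention is meant to affect);
- within-woman correlation r = 0.5;
- a paired test at two-sided 5%;
- a shift d common to all women, and no SSE effect.

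In SD units, SE = √(2(1 − r)/n), which is √(1/n) at r = 0.5. The probability of a significant result is Φ(d/SE − 1.96) + Φ(−d/SE − 1.96).

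| n | SE | d/SE at d = 0.2 | d = 0.1 | d = 0.2 | d = 0.3 |
|---|---|---|---|---|---|
| 300 | 0.058 | 3.46 | 41% | 93% | over 99% |
| 70 | 0.120 | 1.67 | 13% | 39% | 71% |
| 42 | 0.154 | 1.30 | 10% | 25% | 49% |

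With r = 0.7 and d = 0.2 the figures are 99%, 58% and 39%. Whatever the test, the estimated stage difference is off by the full shift d.

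**The same data compared by arm.** A shift common to both arms cancels, so the false-positive rate stays at 5%. The difference detectable with 80% power is (1.96 + 0.84) × √(1 − r²) × √(2/n per arm):

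- 300 per arm, r = 0.5: 2.80 × 0.866 × 0.0816 = 0.20 SD;
- 500 per arm, r = 0.5: 2.80 × 0.866 × 0.0632 = 0.15 SD;
- without baseline adjustment: 0.23 SD and 0.18 SD.

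**The case against.** The strongest reply is that the plan is silent rather than wrong. The stage sentence names no arm, does not say that the comparison is within women and does not exclude controls. A reader might infer that the protocol has deliberately confined anxiety to change from each woman's own baseline. That is the natural reading, because the stages are SSE stages, but the text does not say it. What stands is that no between-arm comparison is specified.

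A reader might also infer that a pandemic trend would be mistaken for an SSE effect. The documents do not support that. They give no anxiety trend, and they plan no significance test for anxiety. The item is described as being about changing moles, so general pandemic worry might move it little. Enrolment over three months also means that stage and calendar date are not identical. The claim has to be that confounding could occur, in either direction.

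The anxiety comparison sits in an exploratory aim, outside the primary and secondary outcomes, and individual distress has its own route. This limits the weight of the point but does not remove it.

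Finally, the between-arm contrast answers a different question. The protocol expects that some controls may start SSE, which may dilute it. It estimates the effect of being assigned SSE education, not of monitoring a mole. Both points are correct, and they are reasons to keep the stage analysis alongside it. The control data are also inferred: the survey itself is not shown, and a mole-specific item may not apply to a control who tracks no mole.

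**Conclusion.** The point holds as a gap in the specified analysis. Followed as written, the plan yields a stage contrast that cannot separate SSE or monitoring from time, regression to the mean, repeated questioning and, at the monitoring stage, selection. The size and direction of the bias are not in the documents. The probabilities of about 93% (300 women) and about 25% to 39% (42 to 70 women) for a 0.2 SD shift show only how readily such a shift could pass for an effect. They rest on the assumed correlation, shift, test and even split.

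It would go too far to conclude that the trial cannot show how SSE education affects anxiety. If the mirrored survey carries the items, the data will exist and only the comparison is missing. No primary or secondary conclusion is affected. The change is worth making because anxiety is the harm set against benefit and the remedy is cheap.

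**What to change.** Add to the analysis section: the main anxiety/cancer-worry analysis compares intervention with control on the monthly scores in all randomised women, adjusted for the baseline score, using only items asked of all women in both arms. Name the scale, and say how missing scores are handled. The multiple imputation already planned for SSE could serve; the rule that counts drop-outs as not performing SSE does not carry over to a score.

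Keep the comparison of baseline, initial SSE and monitoring as a descriptive analysis, reported with the number of women at each stage. Do not replace the all-randomised comparison with one limited to women who have a concerning mole, because that would bring the selection back.

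Before this is fixed, confirm that the control survey contains the same anxiety/cancer-worry items at baseline and each month. If it does, the cost is analysis wording and analysis time, with no added women or visits. If it does not, a general item would have to be added to the online survey in both arms. The small downside is the possible dilution from controls who start SSE, which should be stated when the result is reported.

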Subjects in the intervention arm will monitor new and concerning moles for 4 months by doing monthly skin checks and partner-assisted skin checks (if applicable), record the scores on a scorecard provided in their SSE brochure, and complete the monthly online survey, which asks about changes in mole scores and potential anxiety associated with evolving moles. Subjects will also receive a monthly text message to their personal phone with SSE reminders.

If the subject indicates on their monthly survey or by communicating with the study team, in the form of an email and/or call, that the score of their mole has increased, three options on how to proceed will be offered to the subject. The three choices are as follows: a) continue monthly checking the mole for change, b) receive the mole self-sampling kit to obtain genetic analysis to guide the decision to seek health care, or c) seek an appointment with an HCP.

The mole self-sampling kit contains the materials, directions and a Fed Express or USPS Express mail envelop to overnight the kit to the DermTech laboratory.

Participants may request a kit by email or telephone call to the research team, who will send the kit by Fed Express or USPS Express mail. Within 3-5 business days, the DermTech laboratory will provide the results of the gene analysis online to the PI, [name], who will inform the participant with a written report stating:

- a) the mole is benign, and nothing further is needed or
- b) the mole needs to be biopsied.

If the initial sample has too few cells for analysis, then the participant will be invited to obtain another sample, instructions will be reviewed by telephone or by Facetime with the participant and an additional sample will be obtained.

Participants requiring a skin biopsy will be referred to a local HCP. The research team will develop a participant navigation system for triage to a local HCP, including surgical oncologists, dermatologists, and family practitioners. This triage system will be used to refer participants to schedule an appointment for the skin biopsy within 2-3 weeks. The genetic analysis of the mole will be provided in a letter to the HCP selected by the participant.

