a printed brochure will be mailed. Participants will receive monthly reminders via email and text messaged to their personal phone to perform SSE, to encourage engagement and retention. In addition, a monthly REDCap survey will be sent to the subject's email. This monthly survey will include goal setting and reminders to engage a skin check partner to help check skin in hard to see areas and to assist with the monitoring of any concerning moles and new moles. Tracking of specific details and changes of concerning and new moles will be documented on the provided scorecard in the brochure. If the score of the mole increases, which is indicated on the monthly survey or via email and/or phone, three options on how to proceed with the concerning mole will be provided to the subject.

-Option 1 is to continue monitoring the mole monthly for change.

-Option 2 will be to perform mole self-sampling with the kit to collect a sample of surface cells of the concerning mole with four adhesive patches for gene analysis to help decide about seeking further health care for biopsy of the mole. Of note, physician collected samples tested for *LINC* and *PRAME* gene mutations differentiated melanoma and melanoma in situ from benign moles and were confirmed histologically with 91% accuracy.

-Option 3 will be to seek an appointment with a health care provider.

If mole self-sampling is selected, the kit with the subject number as ID (blinded for personal identifying information), directions, and postage for the kit to be sent to the company that created this self-sampling kit, DermTech, will be provided. Upon completing the mole self-sampling and mailing the specimen to the DermTech laboratory, it will take 3-5 days for the results to be provided to the PI, [name], in the form of a secure online portal. The subject will not obtain their gene test results from the DermTech laboratory. [name] will provide written test results to the participant with the option of discussing the results with a telephone call. A referral will be made to the HCP to perform a skin biopsy if needed. The DermTech self-sampling kit is approved for use but requires ordering by a licensed HCP, who will be [name], the PI.

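### A negative gene result on a self-collected sample is reported as benign with nothing more to do, although no accuracy figure for self-collection is given and the risk section omits false results

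*Combined protocol and SAP*

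**What the plan says.** Study Interventions allows the written report two contents: either "the mole is benign, and nothing further is needed", or the mole needs a biopsy. Sharing Results with Participants repeats the pair (the report says "if the mole is benign and nothing further needs to be done or if the mole needs to be biopsied") and adds: "The same process of sharing results applies to participants and their skin check partners".

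On accuracy, Procedures Involved says that results from physician-collected samples separated melanoma from benign moles and "were confirmed histologically with 91% accuracy". No sensitivity, specificity or negative predictive value is given, and there is no figure of any kind for self-collected samples. The exploratory aim under Objectives is "To assess the feasibility of self-sampling concerning moles for gene assay". Study Endpoints measures it by time to sampling, kits returned and adequacy of cells.

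On the pathway, Study Interventions sends moles scored 8 or 9 to self-sampling in place of the usual appointment within about 2 to 3 weeks. It also says: "Subjects in the intervention arm will monitor new and concerning moles for 4 months by doing monthly skin checks". The monthly survey asks about score changes, and an increase opens three options: keep monitoring, use the kit, or see a health care provider (HCP). After testing, the principal investigator (PI) is to "make a recommendation about the need to obtain a biopsy of the mole, offer to provide a referral to local HCPs", and results come in writing "with the option of discussing the results with a telephone call".

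Risks to Participants covers awareness of risk and anxiety, rates the risks as minimal and expects neither physical nor psychological harm. False results are not mentioned.

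**The concern.** The report gives an unqualified diagnosis and closes the matter. It does so for a mole the participant had already flagged as concerning, on a sample collected in a way whose feasibility the study is still testing. A person whose melanoma was missed would hold a letter from the PI saying that nothing more is required.

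The Background explains why this matters: it gives melanoma growth of about 0.12 mm in depth per month and treats time to presentation as a main determinant of outcome. The brochure also links the word benign with ending checks, for a visual score of 3. A reader trained on the brochure could carry that link over to the gene report. If she stops scoring the mole, the survey trigger that could bring her back to an HCP no longer works for it. In that setting false reassurance is a physical risk, which the risk section does not acknowledge.

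**Working it through.** The plan has no figure of its own to reproduce here. The check is what the 91% can support, and which safeguards reach a false negative.

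**1. The 91% does not fix a miss rate, even for physician-collected samples.** Read as the overall proportion correct,

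accuracy = p × Se + (1 − p) × Sp,

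where p is melanoma prevalence among sampled moles, Se sensitivity and Sp specificity. None of the three is given. Assume p = 5%:
- If Se = 1, then Sp = (0.91 − 0.05) / 0.95 = 0.905.
- If Se = 0, then Sp = 0.91 / 0.95 = 0.958.

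Both give 91% accuracy. One test misses no melanoma and the other misses all of them.

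**2. Scale only, on assumed inputs.** Expected misses = n × p × (1 − Se). Study Endpoints caps n at 100 specimens (repeat samples could make the number of moles smaller). Prevalence and sensitivity are assumptions; Se = 0.91 reads the 91% as sensitivity, and 0.70 allows for an assumed loss from self-collection.

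| Assumed p | Misses at Se = 0.91 | Misses at Se = 0.70 |
|---|---|---|
| 1% | 100 × 0.01 × 0.09 = 0.09 | 100 × 0.01 × 0.30 = 0.30 |
| 5% | 0.45 | 1.5 |
| 10% | 0.9 | 3.0 |

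Under these assumptions the number is small but not zero. Nothing below depends on the table.

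**3. Safeguards, set against a false negative from an adequate sample.**

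| Safeguard | Section | Does it reach such a case? |
|---|---|---|
| Repeat sampling | Study Endpoints; Study Interventions | No; it addresses too few cells |
| PI's biopsy recommendation and referral | Objectives | It follows the result, so a negative report prompts neither |
| Monthly scoring, survey and score-increase trigger | Study Interventions; Procedures Involved | Yes, for enrolled women during the 4 months, if they keep scoring the mole |
| Team contact about next steps; call on request | Risks to Participants; Procedures Involved | Possibly; what would be said is not specified |

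**4. Where the main safeguard runs out.**
- *Maximum score.* Three features scored 1 to 3 give totals from 3 to 9, so a mole already at 9 cannot rise. Risks to Participants words the trigger more broadly, as reporting a concerning mole, but this person has been told that hers is benign.
- *Partners.* Procedures Involved says the process for partners matches that for participants, but does not clearly describe a monthly survey for them.
- *After month 4.* Study Timelines limits later contact to unanswered survey items and questions from the health record review.

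**5. Report against monitoring.** Monthly monitoring has no stated exception for gene-negative moles. Beside the alternative of a biopsy, the negative wording may mean only that no biopsy or referral is needed now. It may also be taken as an end to checking. The text does not settle which.

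**The case against.** The strongest reply is that the protocol already follows a gene-negative mole. Enrolled women keep scoring, the survey asks about changes, and any increase brings back the HCP option. The team also undertakes to be in touch about next steps. This stands: a reader might infer that nothing in the plan could catch a false negative, and the documents do not support that. But the safeguard works only if the recipient goes on checking, which the report's wording may discourage, and it has the three limits shown above.

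A second reply is that the gene test answers only whether a biopsy is needed, so the report is compatible with monthly checks. This also stands. A reader might infer an outright contradiction, or an instruction to stop checking; the text shows ambiguity, and the rule to stop applies to a visual score of 3.

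Third, a reader might multiply 0.12 mm by the 4 months of participation and quote 0.12 × 4 = 0.48 mm as the harm. That assumes 4 months without checking, and 4 months does not bound diagnostic delay. It also ignores the restricted physician access that prompted the kit: how long the same person would otherwise have waited is not given.

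Finally, Procedures Involved describes the kit as approved for use, and the consent form and letter template are not in the file. Approval supplies no accuracy figure for self-collection. The missing forms mean one cannot say that participants are uninformed; they do not change the wording that the protocol prescribes.

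**Conclusion.** The point holds as a defect of wording and risk disclosure. The protocol prescribes an unqualified benign report, for participants and partners, with no accuracy figure for self-collected samples. Its risk section omits false results while stating that no physical harm is expected. The wording could lead a recipient to drop the monthly checks that are the main protection against a missed melanoma. That protection is weakest for partners, for moles already at the maximum score, and after month 4.

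The size of the harm cannot be derived from the documents, and the counts above are illustrations on assumed inputs. Nor do the documents show that the test performs poorly on self-collected samples; they give no figure. Confidence is high on the text itself. How recipients would read the report is a judgement.

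**What to change.** 1. In Study Interventions and Sharing Results with Participants, and in the result letter, replace the negative report for participants and partners with:

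> *This result does not indicate a biopsy now. The test can miss melanoma, and we do not have an accuracy figure for self-collected samples. Keep checking this mole every month and seek care if it changes or still concerns you.*

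2. In Risks to Participants, list false-negative and false-positive gene results as risks, and qualify the statement that no physical harm is expected.

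The cost is a few sentences, somewhat less reassurance for people with a negative result, and possibly a few more HCP visits. Randomization, the primary outcome and the sample size are unaffected.
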